10.7. Statistical methods

Age in years will be computed as the difference between the date of completion of the QoL questionnaire collected at Month 0 and the date of birth.

As this is an exploratory analysis, no adjustment will be done for multiple comparisons (i.e. a 2-sided significance level of 0.05 will be used).

Spearman correlations coefficients will be presented to display the relationships between pairs of variables. In addition, particularly for the QoL variables, the variance inflation factor and the condition indices for testing multicollinearity will be estimated.

A bootstrap analysis will be carried out to evaluate the robustness of the results with respect to the selection of variables in the final multivariate model.

All analyses will be carried out using SAS Version 9.1.3 or later.

GSK vaccines will be responsible for performing the statistical analysis.

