10.7.6.3. Predictive factors for individuals developing HZ

Only subjects in the placebo vaccination group will be included in the analysis of potential predictive factors. A Cox proportional hazards regression model allowing for time-dependent covariates will be fitted to identify which factors are predictive of developing HZ. The model will include time to HZ as the outcome variable and as potential predictors: demographic and clinical characteristics, *SF-36* variables and *EQ-5D* variables. Subjects who did not develop HZ will be censored at the time of their last study visit. The proportional hazards regression model will be used for both minimally adjusted analyses and multivariate analyses. All factors will initially be examined in an age- and sex-adjusted model with stratification for the clinical trial (i.e. ZOSTER-006 and ZOSTER-022). Factors will be included in the multivariate model if they are associated ($P < 0.05$ using a two-sided test) with HZ in the minimally adjusted model. The multivariate model will also include age and gender with stratification for the clinical trial (i.e. ZOSTER-006 and ZOSTER-022). A step-down (backward) variable selection procedure will be used to fit the final multivariate model. This model will be fitted using the PHREG procedure of the *SAS/STAT* package.

Spearman correlations coefficients will be presented to display the relationships between pairs of variables. In addition, particularly for the quality of life variables, the variance inflation factor and the condition indices for testing multicollinearity will be estimated.

In the analysis, the impact of excluding “suspected but not confirmed cases” of HZ will be explored. Three analyses will be performed whereby it will be assumed that “suspected but not confirmed cases” are (1) “Not in at risk group” (2) “In at risk group” and event=0, (3) “In at risk group” and event=1.

Due to the multiple measurements of the *EQ-5D* and *SF-36* over time, repartition in the HZ positive or HZ negative will be dynamic. Subjects who did not develop a confirmed HZ before one-timepoint (Day 0, Month 14, Month 26 and Month 38) will be considered HZ negative at that timepoint, and the characteristics and QoL scores reported for this subject at the previous timepoint will be considered as **not leading** to HZ.

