6.3. Secondary Objectives

6.3.1. SF-36 and EQ-5D

The quality of life questionnaires to be analysed in this study are the SF-36 and EQ-5D. The SF-36 health survey and the EQ-5D questionnaires were to be completed by all subjects at Months 0, 14, 26 and 38 in ZOSTER-006 and ZOSTER-022.

Basic summary statistics (N, Mean, Standard Deviation) of each of the 8 components of the SF-36 Questionnaire (Physical Functioning, Role Physical, Bodily Pain, General Health, Vitality, Social Functioning, Role Emotional and Mental Health) and the EQ-5D Utility and visual analogue scale (VAS) scores will be presented at each scheduled timepoint by country and age group.

In addition, a more detailed statistical analysis, including the median, quartiles and minimum and maximum values, of the 10 components will be presented by timepoint, age-category and gender and will be presented in a separate annex.

The EQ-5D utility will be based on country specific Time Trade-off (TTO) values for the analysis by country. The UK TTO will be used for countries for which there is no specific TTO.

Presenting the data by country will allow for comparison with normative values for those questionnaires in the general population of the countries participating in the study

This analysis will be based on the TVC.

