6.3.4. Predictive factors for subjects developing HZ

A Cox regression model allowing for time-dependent covariates will be fitted to identify which factors are predictive of developing HZ. The model will include time to HZ as the outcome variable, the demographic variables age and gender and the time dependent *SF*-36 variables and *EQ-5D* variables as potential predictors. This analysis will be performed for subjects in the Placebo group in the TVC.

Subjects who did not develop HZ will be censored at the time of their last study visit. The regression model will be used for both minimally adjusted analyses and multivariate analyses. All factors will initially be examined in an age- and gender-adjusted model with further adjustment for the original study (ZOSTER-006 or ZOSTER-022). Factors will be included in the multivariate model if they are associated (P < 0.05 using a two-sided Wald test) with HZ in the minimally adjusted model. The multivariate model will also include age, gender and original study. A step-down (backward) variable selection procedure will be used to fit the final multivariate model. This model will be fitted using the PHREG procedure of the SAS/STAT package.

The parameter estimates and standard error of each SF-36 and EQ-5D parameter from the minimally adjusted model will be presented. The final multivariate model will also be presented.

The analysis will be performed with the event defined as a HZ confirmed case. Three separate analyses will be performed examining the impact of excluding suspected but not confirmed cases.

The first analysis will exclude subjects who had a suspected case that was later proven not to be a HZ episode.

204878 (ZOSTER-064) Statistical Analysis Plan Amendment 1

The second analysis will include all subjects. Those subjects who had a suspected case that was later proven not to be a HZ episode will be censored at their latest available assessment and will be considered not to have had the event.

The third analysis will also include all subjects. The definition of event will be changed to having a suspected case of HZ.

The distribution of confirmed cases of HZ amongst suspected cases will be presented by age group for subjects in the placebo group in the TVC.

Details of the process behind the inclusion of time dependent covariates are included in section 7.4

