7.4. Predictive factors for individuals developing HZ

Only subjects in the placebo group will be included in the analysis of potential predictive factors. A Cox regression model allowing for time-dependent covariates will be fitted to identify which factors are predictive of developing HZ. The model will include time to HZ as the outcome variable, the demographic variables age and gender and the *SF-36* variables and *EQ-5D* variables as potential predictors.

Each EQ-5D and SF-36 assessment at a scheduled time point will be re-classified into time points based on the date of assessment relative to date of vaccination:

Studyday=date of assessment – date of vaccination.

The study day will be time component used in the model.

Since there are a maximum of four SF-36 and EQ-5D assessment times we define the variables T_0 , T_1 , T_2 , T_3 as the study day relative to vaccination (day 0) of the QoL assessment and QoL₀ QoL₁, QoL₂, QoL₃ as the values of the QoL assessment at each timepoint. The value of the time-dependent variable QoLt is equal to QoL₀ if $0 < t \le T_1$, QoL₁ if $T_1 < t \le T_2$, QoL₂ if $T_2 < t \le T_3$, with QoLt = QoL₃ if $t > T_3$.

The above model is implemented in SAS as follows:

```
ODS output ParameterEstimates=PE1;

PROC PHREG DATA=tsurv;

CLASS study gender;

MODEL fu_time*hz_conf(0) = age study gender PFT;

PFT=PF0;

IF fu_time > time1 and time1 ne . then PFT=PF1;

IF fu_time > time2 and time2 ne . then PFT=PF2;

IF fu_time > time3 and time3 ne . then PFT=PF3;

RUN;
```

Spearman correlations coefficients will be presented to display the relationships between pairs of variables. In addition, for the quality of life variables, the variance inflation factor and the condition indices for testing multicollinearity will be estimated.

Example: To illustrate the method the following hypothetical 3 subjects are examined:

Table 5 Data from hypothetical subjects to illustrate time dependent covariates

Subject	QoL0	T0	QoL1	T1	QoL2	T2	QoL3	Т3	Censored /day	Event/ day
PPD	80	0	75	425	65	790	24	1050	Yes/1090	No
	90	0	65	420	50	800	45	1050	No	Yes/480
	98	0	43	435	45	790	45	1060	No	Yes/900

204878 (ZOSTER-064)

Statistical Analysis Plan Amendment 1

Table 6 Resolution of hypothetical subject

Subject PPD	Event	Time Interval	QoL
PPD	0	(0, 425]	80
	0	(425, 790]	75
	0	(790, 1050]	65
	0	(1050, 1090]	24

Subject will be censored at day 1090.

Table 7 Resolution of hypothetical subject

Subject	Event	Time Interval	QoL
PPD	0	(0, 420]	90

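### The only mutually adjusted HZ predictor model is chosen by a P<0.05 screen and backward elimination on the same placebo data, and no planned step corrects its standard errors, so its 95% intervals will be too narrow

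*Protocol*

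**What the plan says.** Protocol 10.7.6.3 and SAP 6.3.4 describe a Cox model with time-dependent covariates in placebo recipients, built in two selection steps.

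- **Screen.** Each factor is tested alone in a model adjusted for age, gender and original study. SAP 6.3.4: "Factors will be included in the multivariate model if they are associated (P < 0.05 using a two-sided Wald test". Protocol 10.7.6.3 sets the same threshold.
- **Elimination.** Protocol 10.7.6.3: "A step-down (backward) variable selection procedure will be used to fit the final multivariate model". The SAP repeats this. No level for staying in the model is given.

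On reporting, SAP 6.3.4 says "The parameter estimates and standard error of each SF-36 and EQ-5D parameter from the minimally adjusted model will be presented" and then "The final multivariate model will also be presented".

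Four further statements bear on the point.

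- Protocol 10.7 on multiplicity: "As this is an exploratory analysis, no adjustment will be done for multiple comparisons".
- Protocol 10.7 on stability: "A bootstrap analysis will be carried out to evaluate the robustness of the results with respect to the selection of variables". SAP 6.3.4 and 7.4 do not mention this bootstrap, and SAP section 9 does not list it among the changes from the planned analyses.
- SAP 7.4 on collinearity: "for the quality of life variables, the variance inflation factor and the condition indices for testing multicollinearity will be estimated". Neither document says what follows if collinearity is found.
- SAP 6.3.1, on descriptive QoL tables, counts the scores: "quartiles and minimum and maximum values, of the 10 components". These are the eight SF-36 scales, EQ-5D utility and VAS.

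**The concern.** A standard error printed for a selected model treats that model as if it had been fixed in advance. Here a scale appears only if its estimate was large enough to pass two tests on the same data. Neither document provides a hold-out sample, shrinkage or a selection-aware interval.

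The candidates also measure overlapping aspects of health. If one scale truly predicts HZ, the others show a marginal association through their correlation with it, and chance can decide which one survives.

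At stake is the answer to which aspects of health status predict HZ once the others are taken into account. The minimally adjusted models hold one score each and cannot answer that. The selected model is the only planned output that addresses it.

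**Working it through.** The documents give no event count, effect size, scale correlation or coverage for this model, so there is no stated figure to reproduce.

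**Inputs from the documents.** Two-sided 0.05 screen (SAP 6.3.4); 10 scores (SAP 6.3.1); about 1,000 suspected cases across both arms and both trials (Protocol 10.4), which is an upper bound on confirmed placebo cases.

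**Assumed inputs.** D = 700 events (400 and 900 also tried); equal pairwise correlation r = 0.5 or 0.7; one truly predictive scale with log HR b = -0.10, -0.18 or -0.34 per SD (HR about 0.90, 0.84, 0.71; reciprocals about 1.1, 1.2, 1.4); elimination at 0.05.

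**Why correlated null scales get in.** The expected screening z is b√D for the true scale and r·b·√D for a null one. With b = -0.10 and √700 = 26.46:

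- true scale: 0.10 × 26.46 = 2.65 in absolute value;
- null scale, r = 0.5: 1.32, so it passes with probability about P(Z > 1.96 - 1.32) = 26%;
- null scale, r = 0.7: 1.85, so it passes with probability about P(Z > 1.96 - 1.85) = 46%.

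Elimination and the interval use the same 1.96 cut-off. So the ordinary interval of any falsely retained scale excludes zero, its true independent effect, by construction.

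**Simulation.** Score vector U ~ N(D·R·b, D·R); screen |U_j|/√D > 1.96; then backward elimination at |z| < 1.96. For a retained set S the estimate is R_SS⁻¹U_S/D with variance R_SS⁻¹/D. Its interval is compared with the independent effect b_j and with the reduced model's own target R_SS⁻¹(Rb)_S.

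Results at 700 events:

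| Quantity | Result |
|---|---|
| Coverage of independent effect, retained scales, all effects | 47% to 81% |
| of which at b = -0.10 | 63% (r = 0.5), 47% (r = 0.7) |
| Coverage of selected model's own target, all effects | 58% to 88% |
| Coverage in the full 10-scale model | 95% |
| Only wrong scales retained, b = -0.10 | 27% to 42% of runs |
| Only wrong scales retained, b = -0.18 | 3% to 14% |
| Only wrong scales retained, b = -0.34 | about 0% |

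At b = -0.10, coverage of the independent effect is 48% and 35% with 400 events, and 67% and 53% with 900 (r = 0.5 and 0.7).

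**Separate run at 600 events, r = 0.75:**

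| HR per SD | Coverage, independent effect | Coverage, own target | Any wrong scale | Only wrong scales |
|---|---|---|---|---|
| 1.1 | 38% | 88% | 47% | 46% |
| 1.2 | 56% | 73% | 38% | 23% |
| 1.4 | 56% | 56% | 38% | <1% |

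With no true predictor, at least one scale reaches the final model in 19% to 33% of runs. Ten independent scales would give 1 - 0.95¹⁰ = 40% passing the screen.

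**Selection-aware spread.** Repeating the screen and elimination in each bootstrap resample (600 events, r = 0.6 to 0.75, HR 1.1 to 1.2) gives a median bootstrap SD of 1.7 to 2.1 times the ordinary standard error. Median inclusion frequency is 46% to 82% for the true scale when selected and 39% to 47% for a wrongly selected one.

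**Price of not selecting.** VIF = (1 + 8r)/[(1 - r)(1 + 9r)]. For r = 0.5 this is 5/2.75 = 1.82; for r = 0.7 it is 6.6/2.19 = 3.01. Standard errors rise by √1.82 = 1.35 and √3.01 = 1.74 relative to uncorrelated scales. Ten scores plus age, gender and study make 13 parameters: 400/13 = 31 and 900/13 = 69 events per parameter.

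**The case against.** **The selected model is not the only output.** A reader might infer that unselected scales disappear from the report. SAP 6.3.4 does not support that: every scale's minimally adjusted estimate and standard error is shown. What remains is that these estimates are not mutually adjusted.

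**A bootstrap and collinearity checks are planned.** The bootstrap addresses instability of the selection, which is half of this point. But it is not said to alter any interval, and the current SAP is silent on it. A reader might infer that it was dropped. The documents do not say so; Protocol 10.7 still contains it, and Protocol 10.9 requires deviations to be justified in the study report. The gap is that the operative plan does not specify it.

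**The work is exploratory.** This is fair, and it limits how serious the point is. It does not make an interval labelled 95% cover 95% of the time.

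**The target is debatable.** The objective is prediction, and a correlated proxy can predict. Judged against the selected model's own target, coverage is better at weak effects (about 88%) but still falls to 58%. For the truly predictive scale, when retained, coverage is 87% to 97% across the runs, so the low overall figures come mainly from falsely retained scales.

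**The full model does not stop false naming.** Some null scale reaches P<0.05 in 35% to 37% of its runs (nine independent tests would give 1 - 0.95⁹ = 37%). It also detects the true scale less often at b = -0.10: 51% against 58% (r = 0.5) and 33% against 43% (r = 0.7). This stands, and it argues for showing both models rather than replacing one.

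**The candidate list is not settled.** Protocol 10.7.6.3 also names clinical characteristics, and neither document defines the EQ-5D variables for this model. The count of 13 parameters depends on the ten scores in SAP 6.3.1.

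**Conclusion.** The point holds in a limited form. The one mutually adjusted model in the plan is selected and estimated on the same data, and neither document corrects its standard errors. The SAP does not specify the interval format for the final model; ordinary PHREG standard errors are assumed here. Under the assumed inputs, undercoverage appears at every effect size tried: 47% to 81% for the independent effect and 58% to 88% for the model's own target, against 95% without selection.

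A reader might go further and conclude that the model will often name the wrong scale. The calculations support that only for weak effects with strongly correlated scales. By log HR -0.34, models with only wrong scales have all but vanished, although extra scales still enter.

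All figures rest on assumed events, correlations and effects, equal correlations, a single true effect, fixed covariates, no age, gender or study terms, and an assumed 0.05 elimination level. They indicate direction and rough size. For an exploratory secondary objective this is a cheap improvement, not a flaw that undermines the study.

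**What to change.** In SAP 6.3.4:

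1. Beside the selected model, report the unselected Cox model with a pre-listed set of scores (eight SF-36 scales, EQ-5D utility, VAS) plus age, gender and study, as HR with 95% CI per SD. Add a joint Wald test of the QoL scales.
2. Label the selected model's intervals as post-selection, and state the elimination level.
3. Restore the protocol's bootstrap. Repeat the screen and the elimination in every resample, and report inclusion frequencies and selection-aware intervals. If it is not to be done, say so with a reason in SAP section 9.

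**Cost.** A few extra model runs, since three case-definition analyses are planned, plus SAP wording; no new data. Full-model intervals are wider (SE × 1.35 to 1.74 under the assumed correlations). Subjects missing any scale drop out of the full model, because SAP 7.5.2 does not impute items. The chance that some null scale reaches P<0.05 is not reduced (35% to 37% of runs), which is why the joint test and the bootstrap are needed alongside.

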10.7.6.4. Analysis of safety by frailty status

This analysis of the safety data from the ZOSTER-064 population will be based on the Total Vaccinated cohort for safety. Solicited, unsolicited and serious adverse events will be analysed by baseline frailty status.

Incidences of SAEs during the 30-day (Days 0 – 29) follow-up period after each vaccination, up to 8 months and during any time during the study classified according to the MedDRA System Organ Class and Preferred Terms will be tabulated by frailty status.

10.7.7. Analysis of immunogenicity

The analysis will be based on the immunogenicity data from the ZOSTER-064 population for subjects in the adapted ATP for analysis of humoral immunogenicity, and for subjects in the TVC for analysis of CMI, respectively (Section 10.5.3).

10.7.7.1. Humoral immune response

Humoral immune response will be assessed and analysed by frailty status in the Humoral Immunogenicity subset.

Descriptive statistics:

If the data allows the following parameters will be tabulated by vaccination group and frailty status at Month 0, Month 3, Month 14, Month 26 and Month 38:

- Geometric mean concentrations (GMCs) of anti-gE/anti-VZV Ab with 95% CIs;
- Humoral seropositivity rates with exact 95% CIs;
- Vaccine response rates with 95% CIs.

10.7.7.2. Cell-mediated immune response

CMI response will only be assessed and analysed in the CMI component of the Immunogenicity subset for subjects in the ZOSTER-006 study.

Descriptive statistics:

For CMI response; provided the data allows, the following parameters will be tabulated by vaccination group and frailty status at Months 0, 3, 14, 26 and 38:

- descriptive statistics of the frequency of CD4 T cell secreting at least two different cytokines (IFN- γ , IL-2, TNF- α , CD40L) to both VZV and gE antigens;

- descriptive statistics of the frequency of CD4 T cell secreting at least IFN- γ and another cytokine (IL-2, TNF- α , CD40L) to both VZV and gE antigens;
- descriptive statistics of the frequency of CD4 T cell secreting at least IL-2 and another cytokine (IFN- γ , TNF- α , CD40L) to both VZV and gE antigens;
- descriptive statistics of the frequency of CD4 T cell secreting at least TNF- α and another cytokine (IFN- γ , IL-2, CD40L) to both VZV and gE antigens;
- descriptive statistics of the frequency of CD4 T cell secreting at least CD40L and another cytokine (IFN- γ , IL-2, TNF- α) to both VZV and gE antigens;
- proportion of responders with exact 95% CI.

10.8. Interpretation of analyses

Comparative analyses will be descriptive with the aim to characterise the difference between groups in the endpoint related to the objective. These descriptive analyses should be interpreted with caution.

10.9. Conduct of analyses

Any deviation(s) or change(s) from the original statistical plan outlined in this protocol will be described and justified in the final study report.

10.9.1. Sequence of analyses

There will be one analysis (final analysis) after completion of the data encoding.

10.9.2. Statistical considerations for interim analyses

All analyses will be conducted on final data and therefore no statistical adjustment for interim analyses is required.

11. ADMINISTRATIVE MATTERS

To comply with ICH GCP or other applicable guidelines, administrative obligations relating to data collection, monitoring, archiving data, audits, confidentiality, ownership and publications must be met.

11.1. Electronic Case Report Form instructions

A validated GSK defined electronic data collection tool will be used as the method for data collection.

In all cases, subject initials will not be collected nor transmitted to GSK. Subject data necessary for analysis and reporting will be entered/transmitted into a validated database or data system. Clinical data management will be performed in accordance with applicable GSK standards and data cleaning procedures.

While completed eCRFs are reviewed by a GSK Biologicals' Site Monitor, omissions or inconsistencies detected by subsequent eCRF (specifically the QoL questionnaires) review may necessitate clarification or correction of omissions or inconsistencies with documentation and approval by the investigator or appropriately qualified designee. In all cases, the investigator remains accountable for the study data.

Once the database is archived and the clinical study report is complete and approved by all parties, each participating investigator will be provided with a CD-ROM of the final version of the data generated at his/her investigational site.

